9 PHARMACOKINETICS AND PHARMACODYNAMICS

All analyses described in [Section 9.1](#) will be performed on the PK-PPS, and all other analysis will be performed on Safety Set.

9.1 Pharmacokinetics

Individual plasma concentrations of rozanolixizumab will be summarized by treatment group and overall for administered RLZ dose and RLZ total and scheduled sampling day for the PK-PPS using n, arithmetic mean, median, SD, minimum, maximum, geometric mean (geomean) with associated 95% CI, and geometric coefficient of variation (geoCV) (assuming log-normally distributed data).

A scatter plot of combined individual concentration versus time profiles will be presented in linear scale by treatment group with all study participants overlaid on the same plot, including day 3, 6, 24, 38, 41. The same plot will also be presented by administered RLZ dose () and RLZ total.

Furthermore, a plot time course plot of geometric mean concentrations by administered RLZ dose will be presented by treatment group and RLZ total. See details in [Section 4.9.3](#).

All figures will include the lower limit of quantification (LLOQ) on the semi-logarithmic plots.

The following rules will apply for PK data listings and summaries:

- Values below the LLOQ will be reported as below the limit of quantification (BLQ)
- Descriptive statistics of concentrations will be calculated if at most 1/3 of the individual data points at a timepoint are missing or are not quantifiable (<LLOQ). Values that are BLQ will be replaced by the numerical value of the LLOQ/2 in this instance. If more than 1/3 of the individual data points at a timepoint are missing or are not quantifiable, then only n, minimum, median and maximum will be presented. The other descriptive statistics will be left blank.
- If $n < 3$, then only the n, minimum and maximum will be presented. If no study participants have data at a given timepoint, then only $n=0$ will be presented.

- The 95% CI lower and 95% CI upper should be left blank if the SD (or equivalently, the geoCV) is 0

The geoCV will be calculated using the following formula where SD is the standard deviation from the log-transformed data $\text{geoCV}(\%) = \sqrt{\exp(\text{SD}^2) - 1} \times 100$.

Individual concentrations of rozanolixizumab will be listed by treatment group and RLZ total for the PK-PPS and will include the actual sampling time in days relative to the previous dose, the IgG observed at the same visit, the ADA titer observed for the binding assay and the NAb titer for the same visit, and change from Baseline in total IgG and IgG subclasses for the corresponding visit.

9.2 Pharmacodynamics

9.2.1 MG-specific autoantibodies

MG-specific autoantibodies (anti-MuSK/anti-AChR) Baseline values will be based on the last available assessment value prior to first IMP (excluding historical data collected on CRF since the assays were not from the same vendor as specified in this study).

MG-specific autoantibodies (anti-MuSK/anti-AChR) will be summarized by treatment group and RLZ total at scheduled visit for observed values, absolute and percentage changes from Baseline. Additional summary of absolute and percentage changes from Baseline in MG-specific autoantibodies (anti-MuSK/anti-AChR) will be performed by weight subgroup and total for administered dose and RLZ total at scheduled visit (reference Section 4.9.3). The maximum decrease from Baseline in MG-specific autoantibodies (change and percentage change) will be reported in the listing and summarized for each treatment.

Mean and mean percentage change from Baseline values in MG-Specific autoantibodies will be plotted over time by treatment, RLZ total and period with all treatments overlaid on the same plot and the plot will be repeated for the following dose groups: placebo, [REDACTED].

Mean percent change from baseline of anti-MuSK and Total IgG, and mean change from baseline of MG-ADL, QMG, MG-C will be plotted over time by treatment and RLZ total for only participants who are anti-MuSK positive at baseline; Additionally, data from individual study participant will be plotted representing percentage change from Baseline in anti-MuSK and Total IgG, and MG-ADL, QMG, MG-C change from Baseline for only participants who are anti-MuSK positive at baseline. The same plots will be repeated for percentage change from Baseline values in anti-AChR for only participants who are anti-AChR positive at baseline.

A boxplot of maximum percentage change from Baseline for MG-specific autoantibodies will be plotted by the following dose groups: placebo, [REDACTED].

MG-specific autoantibodies will be listed, together with total IgG, IgG subclasses, MG-ADL, QMG, MG-C change from Baseline.

The correlation between screening and Baseline assay (positive, negative) will be presented based on the Pearson correlation test.

9.2.2 Total serum IgG and IgG subclasses

Total serum IgG concentrations and IgG subclasses will be summarized by treatment group, RLZ total and time point for observed values, change from Baseline, and percentage change from Baseline. Additional summary of absolute and percentage changes from Baseline in total IgG will be performed by weight subgroup and total for administered dose and RLZ total at scheduled visit (reference section 4.9).

The maximum change and percent change from Baseline in total serum IgG and IgG subclasses will be reported in the listing and summarized for each treatment. In the event that a decrease from Baseline in total serum IgG or IgG subclass is not observed in a given study participant, the maximum change will be reported as the smallest increase from Baseline.

Mean change and percent change from Baseline values in total serum IgG will be plotted over time by treatment and RLZ total with all treatments overlaid on the same plot, and the plot will be repeated by the following dose groups: placebo, [REDACTED].

Spaghetti plots will be provided for total IgG and percentage change from baseline in total IgG over time stratified by treatment group, RLZ total and Baseline bodyweight group (<50kg, 50kg-<70 kg, 70-<100kg, ≥100kg) where the Baseline bodyweight group is multipaneled or overlaying with different colors within each treatment group.

For correlation analysis between clinical endpoints and PD data, scatterplots including regression lines and correlation coefficients will be provided for:

- Maximum change from baseline through to and including day 43 in total IgG versus change from baseline at day 43 in MG-ADL, QMG, and MG-C scores;
- Maximum percent change from baseline through to and including day 43 in total IgG versus change from baseline to day 43 in MG-ADL, QMG, and MG-C scores;
- Minimum total IgG through to and including day 43 versus change from baseline to day 43 in MG-ADL, QMG, and MG-C scores.

A boxplot of maximum percentage change from Baseline for total IgG will also be plotted by the following dose groups: placebo, [REDACTED].

Serum concentration of change from Baseline in total IgG and IgG subclass will be listed together with concentrations of rozanolixizumab, ADA status and MG-ADL change from Baseline, as specified in [Section 9.3.2](#). In addition, it will be listed with IgG subclasses and MG-specific autoantibodies as described in [Section 9.2.1](#).

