2 INTRODUCTION

Rozanolixizumab is a humanized IgG4 monoclonal antibody that is being developed as an inhibitor of the activity of the FcRn for IgG.

By blocking the activity of FcRn, rozanolixizumab accelerates the catabolism of IgG antibodies, including IgG pathogenic autoantibodies. The aim is to reduce the concentration of pathogenic IgG in patients with autoimmune diseases mediated by the action of IgG autoantibodies.

The FcRn recycles IgG and albumin and transports it bidirectionally across epithelial barriers. Recent studies have shown that FcRn rescues both IgG and albumin from intracellular lysosomal degradation by recycling it from the sorting endosome to the cell surface (Roopenian and Akilesh, 2007). FcRn may also mediate transcytosis of IgG to facilitate its distribution within tissues. Rozanolixizumab has been specifically designed to block IgG binding to FcRn without blocking the binding and recycling of albumin.

Rozanolixizumab binds with high affinity to FcRn at both neutral and acidic pH. Immunoglobulin G that is constitutively taken up by pinocytosis into cells fails to bind to FcRn, even at the acidic pH found in the endosome. It is therefore not recycled and is trafficked to the lysosomes for degradation.

Production of pathogenic IgG autoantibodies is the major pathophysiology leading to a number of autoimmune diseases, which include MG, pemphigus vulgaris, immune thrombocytopenia (ITP), Goodpasture's syndrome, neuromyelitis optica, Guillain-Barré Syndrome, and chronic inflammatory demyelinating polyradiculoneuropathy.

As individual disease entities, IgG autoantibody-mediated conditions are relatively rare. Treatment of these disorders remains a difficult clinical problem, requiring in many of these conditions the long-term use of corticosteroids alone or combined with other immunomodulatory therapy. These therapeutic approaches are not effective in all patients and conditions and have broad immunosuppressive effects causing considerable toxicity and treatment-related morbidity.

Treatments aimed at reducing the quantity of circulating IgG autoantibodies, including plasmapheresis, immunoadsorption, or high dose IVIg, are being used for primary and secondary therapy of autoimmune diseases. The therapeutic approach of these treatments is thought in part to be based on lowering levels of pathogenic autoantibodies, which represents rational and effective treatment modalities of autoimmune diseases.

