active for MG0007, no further participants will enroll in MG0004 and the study will be closed at the site once all eligible study participants have discontinued MG0004 and had the opportunity to rollover into MG0007.

The maximum duration of the study per study participant will be up to 18 weeks, consisting of a Screening Period (1 to 28 days to account for central laboratory turn-around time), a Treatment Period (6 weeks), and a blinded Observation Period (8 weeks).

1. All study participants who complete the 6-week Treatment Period will roll over into an 8-week Observation Period.
2. All eligible study participants who complete the Observation Period will be invited to be re-randomized into an OLE study to either active dose arm 1 or 2.
3. Study participants who experience disease worsening during the 6-week Treatment Period (eg, an increase of 2 points on the MG-ADL or 3 points on the QMG scale between two consecutive visits) may be considered for rescue therapy (IVIg or PEX) at the discretion of the Investigator.
4. Study participants who need rescue therapy during the 6-week Treatment Period will receive IVIg or PEX and complete any subsequent visit(s). No further infusions of rozanolixizumab will be administered after initiation of rescue therapy. Once the participant completes Visit 10, he or she will move into the 8-week Observation Period.
5. Study participants who complete the Treatment Period and require initiation of rescue therapy after they start the 8-week Observation Period, may either opt to receive IVIg or PEX or complete the EOS visit and immediately roll over into an OLE study where the participant will receive rozanolixizumab. Study participants who opt to receive IVIg or PEX will complete any remaining visits in the Observation Period and will not be invited to join an OLE study.
6. Study participants who did not complete the 6-week Treatment Period because they needed rescue therapy and require initiation of a second course of rescue therapy while in the 8-week Observation Period can roll over to an OLE study if a minimum of 2 weeks have lapsed since completion of the last IVIg or PEX session. The EOS visit must be completed before enrolling into an OLE study. Alternatively, they can be treated with IVIg or PEX. Study participants who opt to receive IVIg or PEX will complete any remaining visits in the Observation Period and will not be invited to join an OLE study .

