9.4.4 Anti-tetanus toxoid serum titers

Anti-tetanus toxoid serum titers will be summarized by treatment group, RLZ total and visit for both absolute values, change from Baseline, and percent change from Baseline.

The geometric mean change from Baseline with 95% CI in anti-tetanus toxoid serum titers versus time at each scheduled timepoint will be plotted by treatment group excluding all participants with undetectable Baseline titers. IgG values will be overlaid on the same plot.

Measurements BLQ will be imputed with half of the LLOQ for the purpose of calculating change from Baseline. Measurements, if applicable, will be imputed to the upper limit of quantification.

Anti-tetanus toxoid serum titers will be listed.

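### The pharmacodynamic and anti-tetanus summaries have no rule for samples taken after IVIg or plasma exchange rescue, so they can describe the rescue as well as the drug.

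*SAP*

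**What the plan says.** SAP 2.1.3 gives the objective as the effect of rozanolixizumab on IgG and disease-specific autoantibodies, and has a separate objective for its effect on tetanus IgG antibodies.

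For IgG, SAP 9.2.2 says: "Total serum IgG concentrations and IgG subclasses will be summarized by treatment group, RLZ total and time point for observed values", followed by change and percent change. For autoantibodies, SAP 9.2.1 says that they "will be summarized by treatment group and RLZ total at scheduled visit for observed values, absolute and percentage changes from Baseline". SAP 9.4.4 says: "Anti-tetanus toxoid serum titers will be summarized by treatment group, RLZ total and visit for both absolute values", again with changes. On the analysis set, SAP 9 states that apart from pharmacokinetics "all other analysis will be performed on Safety Set"; SAP 9.4 also names the Safety Set.

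Extremes are reported too. SAP 9.2.1 summarises "The maximum decrease from Baseline in MG-specific autoantibodies", and SAP 9.2.2 the maximum change in IgG. The by-treatment summaries and boxplots of these extremes state no time window. The scatterplots against MG-ADL, QMG and MG-C do state one, for example "Maximum percent change from baseline through to and including day 43 in total IgG".

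Protocol 6.5.4 defines rescue as IVIg or PEX. Under Protocol 4.1, rescue in the Treatment Period ends study drug but not the visits. Participants who choose IVIg or PEX in the Observation Period also complete its remaining visits.

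**The concern.** Rescue acts on the quantities being measured. The Protocol Introduction describes "Treatments aimed at reducing the quantity of circulating IgG autoantibodies, including plasmapheresis, immunoadsorption, or high dose IVIg" as therapies for autoimmune disease. IVIg is itself immunoglobulin G, so it adds to measured total IgG. A sample drawn after rescue in the Treatment Period therefore reflects a stopped study drug plus a second treatment acting on the same analytes.

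Three things are at stake. PEX in a placebo participant can produce a drug-like fall. IVIg during the Observation Period, which Protocol 4.2 set up to follow antibody recovery, can look like IgG recovery. And because a maximum decrease or a minimum is fixed by one sample, a single post-PEX value can set a participant's result.

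**Working it through.** **1. Where the documents handle rescue.**

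- SAP 8.1 sets data after rescue before Day 43 to missing, or applies a composite or treatment policy strategy, for the analyses named in SAP 8.2 and 8.3.
- SAP 4.2.1 counts rescued participants as non-responders for binary efficacy endpoints. SAP 8.4.3 censors time to response at rescue.
- SAP 3.4 uses protocol deviations to remove data only from the PK Per-Protocol Set.
- SAP 9.2.1, 9.2.2 and 9.4.4 contain no exclusion, censoring or flag.

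Carrying the SAP 8.1 rule over would not be enough, because its rescue event stops at Day 43 and sampling does not.

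**2. Samples exposed.** Post-Baseline draws in Protocol 1.3:

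- IgG: Visits 4, 5, 6, 8, 9, 10, 12, 14 (8 samples)
- Autoantibodies: Visits 5, 8, 10, 12, 14 (5 samples)
- Anti-tetanus: Visits 10, 14 (2 samples)

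These are upper limits per rescued participant.

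**3. By-visit means.** The plan gives no figure to reproduce, no rescue rate and no post-rescue shift, so the following is an illustration. Shift in arm mean = fraction rescued × per-person shift in percent change from Baseline. The assumed per-person shift runs from -60 points (PEX) to +100 points (IVIg).

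| Fraction rescued | × -60 | × +100 |
|---|---|---|
| 0.02 | -1.2 | +2.0 |
| 0.05 | -3.0 | +5.0 |
| 0.10 | -6.0 | +10.0 |

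For scale, Protocol 4.2 reports a maximal mean IgG reduction of about 43% with subcutaneous dosing in the first-in-human study.

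**4. Maximum decrease.** A simulation used three arms of 80, six Treatment Period visits and 400 repetitions. It assumed:

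- a mean drug effect on IgG reaching -43%, and none on placebo;
- rescue in 10% of placebo and 5% of active participants;
- a post-rescue IgG shift of -50 points for PEX and +60 for IVIg.

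The placebo mean of maximum decrease moved by -4.8 points if all rescue was PEX, -2.2 if half was PEX, and +0.4 if all was IVIg. A later rise does not erase a fall already sampled, so this variable responds mainly to PEX.

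**5. Correlation with Day 43 MG-ADL.** The same simulation assumed mean MG-ADL changes of -3.0 (active) and -1.0 (placebo), SD 3.5, and a further 2-point improvement after rescue. With all rescue by PEX:

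- all data kept: 0.258
- IgG window ended at rescue, post-rescue score kept: 0.208
- rescued participants dropped: 0.235

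The effect is modest. Cutting only the IgG side left the correlation further from the rescued-dropped value (0.235 - 0.208 = 0.027) than keeping everything did (0.258 - 0.235 = 0.023). The rule must therefore cover both members of the pair.

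**The case against.** The best defence is that observed-value summaries are a legitimate descriptive choice for endpoints outside the multiplicity procedure. Medians, boxplots and individual plots are planned, and rescue use is itself summarised, so a reader could see some of the distortion. Excluding post-rescue samples also has a price: it removes data from participants who worsened, which is a selection made after randomisation and related to outcome. That last argument stands, and it is why both versions should be shown. The others limit the importance of the point but do not supply the missing rule.

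Several stronger readings are tempting and are not supported:

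- *That the SAP instructs analysts to keep post-rescue samples.* It is silent. They enter because the observed-value and untimed maximum rules would take them in.
- *That IVIg hides the maximum fall in IgG.* In general it does not (step 4).
- *That PEX creates a spurious IgG-efficacy correlation.* SAP 9.2.2 does not say whether Day 43 scores after rescue are observed or set to missing. If missing, participants rescued before Day 43 leave the plots and the problem goes with them. The direction is also uncertain: rescue follows worsening, so low IgG could sit beside poor scores.
- *That the drug-placebo difference is understated by the whole post-PEX fall times the PEX rate*, for example 0.15 × 70 = 10.5 points. Only the excess over the maximum fall that would have occurred anyway counts; with an assumed 10-point natural fall this is 0.15 × (70 - 10) = 9.0. PEX in active arms would offset it further.
- *That IgA, IgE and IgM (SAP 9.4.3) need the same rule.* No argument for that has been made here.

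**Conclusion.** The gap is real and worth closing. Followed as written, SAP 9.2.1, 9.2.2 and 9.4.4 mix the effect of rescue into summaries meant to show the effect of rozanolixizumab. By-visit means are open to distortion by either rescue, and the extremes mainly by PEX. The correlations are exposed only if observed post-rescue scores are used.

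The size cannot be fixed from the documents. The -6 to +10 point range for the by-visit mean percent change in IgG rests on assumed rescue rates of 2-10% and assumed per-person shifts; at 2% rescued it is only -1.2 to +2.0. The simulated correlations rest on further assumptions and differ little.

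The endpoints are descriptive and classed as other endpoints, so no primary or secondary efficacy test changes. Anti-tetanus titers fall under their own objective in SAP 2.1.3, not the pharmacodynamic one. The population PKPD analysis has a separate Data Analysis Plan that is not among the documents, so its handling of rescue cannot be judged.

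**What to change.** In SAP 9.2.1, 9.2.2 and 9.4.4, present the by-visit summaries, the maximum and minimum change, and the plots with samples taken after the start of the first IVIg or PEX excluded, next to the all-samples version. Flag post-rescue samples in the listings. State the time window for every maximum or minimum.

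For the Day 43 correlations, end the IgG window at rescue and use only pairs in which neither the IgG value nor the clinical score follows rescue. State this for MG-ADL, QMG and MG-C.

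The cost is a short SAP rule and a date filter. Protocol 6.5.4 already requires the date and time of rescue to be recorded, and SAP 8.4.1 identifies rescue from the case report form. The downside is fewer late-visit samples, and an excluded version that follows participants only up to rescue and so describes a selected group at late visits. Showing both versions makes that visible.

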9.3 Anti-drug antibody status

Evaluation of rozanolixizumab immunogenicity will be performed using data from all evaluable study participants in the SS, defined as all study participants treated with rozanolixizumab who have an evaluable pretreatment (baseline) sample (negative or positive ADA sample status), and at least 1 evaluable post-baseline value.

Study participants with an evaluable pretreatment (baseline) sample but without a single evaluable sample taken post-baseline will be included in the reporting of pre-existing ADA but excluded from all other immunogenicity analyses.

The ADA of rozanolixizumab will be measured using a three-tiered assay approach: screening assay, confirmatory assay and titration assay. Any sample confirmed positive for ADA will be assayed to determine whether there is neutralizing potential. Samples that are neutralizing antibody (NAb) positive will be evaluated in a titration assay to quantify the NAb level and will be reported as titer. Samples from study participants on placebo will not be tested for anti-drug antibodies.

9.3.1 ADA Data Consideration

ADA Sample Status

The ADA sample status will be determined for each pre-treatment (Baseline) and post-treatment (post-Baseline) visit where samples are taken for ADA analysis.

- Sample values that are either ‘negative screen’ or the combination of ‘positive screen’ and ‘negative immunodepletion’ will be defined as **ADA negative** if corresponding rozanolixizumab concentrations are equal or below the validated drug tolerance limit of the ADA assay (200µg/mL rozanolixizumab) allowing detection of 100ng/mL ADA
- Sample values that are either ‘negative screen’ or the combination of ‘positive screen’ and ‘negative immune-depletion’, but with corresponding rozanolixizumab concentrations above the validated drug tolerance limit of the ADA assay, will be defined as **ADA inconclusive**
- Sample values that are ‘positive screen’ and ‘positive immunodepletion’ will be defined as **ADA positive**
- Samples that could not be tested for ADA status due to inadequate sample volume, mishandling, or errors in sample collection, processing, storage, etc., will be defined as **Missing**.

NAb sample status (positive/negative/missing) will be determined for ADA positive samples.

ADA Baseline

By default, the Day 1 will be the Baseline value if the ADA sample status at screening is ADA negative or missing. If the ADA sample status at screening is ADA positive and ADA status at Day 1 is ADA negative or missing, the screening will be the Baseline value. If the ADA sample status at screening and Day 1 are the same, Day 1 will be the Baseline value.

ADA /NAb Participant Status

The ADA participant status will be classified on study participant and group level as outlined below (Shankar et al. 2014; Rup et al, 2015). A description of how study participants will be categorized for the immunogenicity assessment is provided in [Table 9–1](#).

Individual study participants will be assessed for ADA participant status, composed of 6 categories: ADA negative, inconclusive, and ADA positive, whereby a positive participant’s status is determined as originating from a treatment-induced, boosted, reduced or unaffected ADA response.

Study participants who are identified as being treatment-induced or treatment-boosted ADA-positive will be grouped as treatment-emergent (TE)-ADA positive participants. Study participants who are identified as being treatment-reduced or treatment-unaffected ADA-positive will be grouped as non-TE-ADA positive participants. Both TE-ADA positive and non-TE-ADA positive participants will be further classified as NAb negative or NAb positive.

The individual and combined ADA participant categories will be summarized through the end of the 8-week observation week (Day 99), unless specified otherwise.

Table 9–1: Terms and Definitions for ADA Evaluation in Study Participants

Classification	Classification Label	Definition
Individual participant categories		
1	Pre-ADA negative – treatment induced ADA negative (ADA-NEG)	Study participants who have an ADA negative sample at Baseline and all sampling points post-Baseline up to the timepoint of interest.
2	Inconclusive	Study participants who have an ADA positive or negative Baseline sample and some post-Baseline samples are missing or inconclusive, while other post-Baseline samples are ADA negative up to the timepoint of interest.
3	Pre-ADA negative – treatment induced ADA positive (TI-POS)	Study participants who have an ADA negative sample at Baseline and have least one ADA positive sample at any sampling point post-Baseline up to the timepoint of interest.
4	Pre-ADA positive – treatment boosted ADA positive (TB-POS)	Study participants who have an ADA positive sample at Baseline and at least one ADA positive sample at any sampling point post-Baseline up to the timepoint of interest, with increased titer values compared to Baseline (greater than a predefined fold difference increase from Baseline value which will be defined within the validation of the assay i.e. MSR of the assay ^a).
5	Pre-ADA positive – treatment reduced ADA positive (TR-POS)	Study participants with an ADA positive sample at Baseline, and ADA negative samples at all sampling points post-Baseline up to the timepoint of interest.
6	Pre-ADA positive – treatment unaffected ADA positive (TU-POS)	Study participants with an ADA positive at Baseline and an ADA positive sample at any sampling point post-Baseline up to timepoint of interest with titer values of the same magnitude as Baseline (less than a predefined fold difference from the Baseline value which will be defined within the validation of the assay, i.e. MSR of the assay ^a).
Combined participant categories		

7	Treatment emergent ADA positive (TE-POS)	Includes study participants who are treatment induced ADA positive (category 3) or treatment boosted ADA positive (category 4).
8	Non-treatment emergent ADA positive (Non-TE-POS)	Includes study participants who are treatment reduced ADA positive (category 5) or treatment unaffected ADA positive (category 6).
9	Treatment emergent ADA positive – NAb positive (TE-POS, Nab-POS)	Includes study participants who are treatment emergent positive (category 7) and have at least one NAb positive sample
10	Treatment emergent ADA positive – NAb negative (TE-POS, Nab-NEG)	Includes study participants who are treatment emergent positive (category 7) and have no NAb positive samples
11	Non-treatment emergent ADA positive-- NAb positive (Non-TE-POS, NAb-POS)	Includes study participants who are non-treatment emergent positive (category 8) and have at least one NAb positive sample
12	Non-treatment emergent ADA positive-- NAb negative (Non-TE-POS, NAb-NEG)	Includes study participants who are non-treatment emergent positive (category 8) and have no NAb positive samples

^a The fold difference increase from baseline value, i.e. the minimum significant ratio (MSR) determined during assay validation, will be reported in the relevant tables, listings and figures. It reflects the fold difference in titer level that considered higher than the assay variation in titer determination

